--	------------------------------------------------------------------------------------------------------------------------------------------------------------------------------------------------------------------------------------------------------------------------------------------------------------------------------------------------------------------------------------------------------------------------------------------------------------------------------------------------------------------------------------------------------------------------------------------------------------------------------------------------------------------------------------------------------------------------------------------------------------------------------------------------------------------------------------------------------------------------------------------------------------------------------------------------------------------------------------------------------------------------------------------------------------------------------------------------------------------------------------------------------------------------------------------------------------------------------------------------------------------------------------------------------------------------------------------------------------------------------------------------------------------------------------------------------------------------------------------------------------------------------------------------------------------------------------------------------------------------------------------------------------------------------------------------------------------------------------------------------------------------------------------------------------------------------------------------------------------------------------------------------------------------------------------------------------------------------------------------------------------------------------------------------------------------------------------------------------------------------------------------------------------------------------------------------------------------------------------------------------------------------------------------------------------------------------------------------------------------------------------------------------------------------------------------------------------------------------------------------------------------------------------------------------------------------------------------------------------------------------------------------------------------------------------------------------------------------------------------------------------------------------------------------------------------------------------------------------------------------------------------------------------

Other Related Risks:

Metabolic Surgery: MS carries a risk for complications and nutritional deficiencies. Both Roux-en-Y gastric bypass and sleeve gastrectomy surgeries have similar risks. Abdominal hernias are the most common complications requiring follow-up surgery. Rare complications include leakage through staples or sutures, ulcers in the stomach or small intestine, blood clots in the lungs or legs, stretching of the pouch or esophagus, persistent vomiting and abdominal pain, inflammation of the gallbladder, and failure to lose weight (very rare).

Psychological: The patients may have anxiety related to the course of their disease and/or the requirement for invasive surgery and medication side effects.

Risk Classification: The study risk cannot be classified as minimal.

Minimizing Risks:

Continuous monitoring by the PIs will minimize all potential risks and discomforts. Research participants will be immediately withdrawn from the study upon evidence of any significant adverse event.

Potential Benefits:

There is no direct benefit to the participants, but knowledge may be gained that will benefit others. Participants will receive body composition reports which will include their bone density, fat mass, and lean mass estimates, leaving them informed of new and useful health information.

Payment for Participation:

Participants will receive \$100 for each complete study visit, totaling \$200 for both visits. If a participant does not complete both visits, they will only be compensated for the visits they have completed. There is no compensation for the time spent on screening.

Financial Obligations of the Subjects:

Pennington Biomedical Research Center and the study Sponsor are not responsible for these costs.

Emergency Care and Compensation for Research-Related Injury:

No form of compensation for medical treatment is available from the Pennington Biomedical Research Center. In the event of injury or medical illness resulting from the research procedures participants will be referred to a treatment facility. Medical treatment may be provided at their expense or at the expense of their health care insurer (e.g., Medicare, Medicaid, Blue Cross-Blue Shield, Dental Insurer, etc.) which may or may not provide coverage.

Vulnerable Populations

This research does not involve individuals who are vulnerable to coercion or undue influence. We will seek consent only under circumstances that provide the prospective participant with an adequate opportunity to consider whether or not to participate. Once enrolled, a participant can voluntarily withdraw at any time point during the study.

Setting and Resource Available

Selection of study site: The study will be conducted at the Metamor Institute and PBRC which has a proven record of recruiting and treating patients with severe obesity. In 2023, the Metamor Institute had 1215 bariatric surgery outpatient clinic visits and performed 420 surgeries.

Experience in metabolic surgery in patients with severe obesity.

[name] is a pioneer of metabolic surgery (MS), has refined the techniques and approaches for patients with severe obesity.

In 2023, the total number of sleeve gastrectomy and gastric bypass procedures performed at Metamor were 201 and 117 cases, respectively. Majority (70%) of these patients have severe obesity (BMI \geq 40) and more than 70% were female.

Metamor Clinic (Jan-Dec 2023)	
Total Number of Outpatient visits	
Obesity Medicine	5000
Bariatric Surgery	1215
Dietitian	2520
Clinical Psychologist	1680
ANNUAL TOTAL	10 415 patients

2023 Metabolic Surgery Volumes

OLOL RMC	Total Volume	Sleeve Gastrectomy	Gastric Bypass	Duodenal switch/ SADI	Revisions/ Conversions
Total Cases	420	201	117	5	72

This pilot study leverages the expertise at the Metamor Institute, the Metabolism and Body Composition Laboratory and the Biomedical Imaging Center, at PBRC. By integrating knowledge from metabolic surgery, metabolism, advanced imaging, we aim to develop an innovative approach to assessing body composition outcomes in metabolic surgery patients. This collaboration will enhance the robustness and applicability of our findings. With state-of-the-art facilities and robust institutional support, PBRC provides the ideal environment to achieve our research goals. Our well-structured and highly skilled team collaboration is uniquely equipped to conduct this pilot research and deliver meaningful outcomes.

Metamor census: Metabolic Surgery (Jan-September 2023)							
Total Patients	BMI \geq 40	Female	Male	African American	White	Asian	Others
306	216	192	24	125	89	1	1

Prior Approvals

There is no prior approval.

Data Collection, Storage and Confidentiality

All results will be kept in locked cabinet files and/or restricted-access computers. All of those will be kept separate from records with names and other personal information. No information about them, or provided by them during the research, will be disclosed to others without their written permission, except if it is necessary to protect their rights or welfare (for example, in case of injury or emergency care), or if it is required by law. When the results of the research are published or discussed in conferences, no information will be included that would reveal the identity of these subjects. All data will be kept in locked files, and subjects will be identified by codes when the data gathered in this procedure is presented or published.

PRIVACY & CONFIDENTIALITY

Where and how data or specimens will be stored locally? Data will be stored on Pennington servers as part of the computer cloud computing system.

How long will the data or specimens be stored locally? Identifiable data will be stored for 5-years following the completion of the study. Deidentified versions of the data will be stored indefinitely.

Who will have access to the data or specimens locally? Only the research personnel and PI will have access to study data. Password protected imaging and laboratory data will be kept locally at Pennington.

Who is responsible for receipt or transmission of the data or specimens locally? All data specimens will be kept locally at Pennington Biomedical.

What information will be included in that data or associated with the specimens? All specimens will be assigned a de-identified study number and stored with that number for location purposes.

Where and how data or specimens will be stored? De-identified data will be stored indefinitely on password-protected computers. Only the PI and co-investigators will have access to the full data during the study.

How long will the data or specimens be stored? Electronic, de-identified data will be stored indefinitely on password protected computers. De-identified biological samples will be stored indefinitely.

Provisions to Protect the Privacy Interests of Subjects

Describe the steps that will be taken to protect subjects' privacy interests. Usual care and conduct of research studies at Pennington Biomedical involves a large team of many different individuals and providers. However, participants choosing to participate in this study will have contact with the research staff as necessary to participate in the study. Most of the staff will not have access to their full PHI but will only have the relevant information on their testing or necessary information for safety purposes. Only the PI will have access to all protected health information as well as data gathered for research purposes. Other provisions to protect privacy will include health history or exam result discussions in a private area and asking any accompanying family members/acquaintances to temporarily leave the room.

Economic Burden to Subjects

There are no costs that participant may be responsible for because of participation in the research.

Consent Process

Prior to undergoing any study procedures, participants will be consented in a private room. These interactions will be kept confidential, and records maintained in a secure, designated location at each facility. A trained member of the study team (investigators, study research coordinator) will review the protocol. Interested participants will be given time to ask any questions about the study procedures. Informed written consent will be obtained from the participant. They will be informed that there will be no consequences if they decide not to enroll in the study and, if they enroll, they may withdraw from the study at any point with penalty.

References:

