Bioimpedance Analysis (BIA)	X	X
Abdomen, Pelvis and Thigh MRI	X	X

Pre-visit requirements:

Participants will fast at least 8 hours prior to their study. Participants will not exercise, shower, or use steam rooms or saunas at least two hours before evaluation.

Participants will bring their own form-fitting clothing attire that does not have metal- containing objects, like zippers, buttons, etc. We can provide clean linen for those that do not have form-fitting clothing attire. Patients will be asked to refrain from ingesting any dyes, calcium or barium supplements as this may affect DXA results.

In-person Measurements:

Each procedure and the measurement tool are listed down in sequence. A summary of the in-person measurements is described in table 1. The following body composition procedures will take place at the outpatient clinic (Clinical Trials Unit Core) at PBRC.

Table 1: In-person study measurements breakdown			
Sequence	Procedure	Time	Total time
Arrive at PBRC	Consenting Process	20m	20m
Outpatient Clinic	Vital signs; Fasting blood work, Urine testing (pregnancy test in women of childbearing age)	30m	50m
Baseline Measurements	Body Weight/Height	10m	1h
Isotopes	Drink Deuterium then Bromide dilutions.	10m	1h10m
Questionnaires	Complete diet and physical activity questionnaires	20m	1h30m
Dual-Energy X-ray Absorptiometry (DXA)	Measure body composition	20m	1h50m
BodPod	Measure body volume	20m	2h10m
3D Optical imaging	Automatically measure body dimensions with several devices	30m	2h40m
Anthropometrics	Waist Circumferences with tape measure	20m	3h
Six-minute Walk	Measure distance to complete 6 minutes of walking	20m	3h 20m
Muscle Strength & Endurance measure	Measure leg strength and endurance	30m	3h 50m
Outpatient Clinic	Blood samples follow up (collected at 4h post- dose)	20m	4h10m
Bioimpedance Analysis (BIA)	Measure body composition with several devices	20m	4h30m
Abdomen, Pelvis and Thigh MRI	Measure skeletal muscle, visceral and subcutaneous fats	40m	5h10m
Complete Study Measurement			

Study Timelines

The duration anticipated to enroll and complete data collection is 8 months after the IRB has been approved. These milestones will help ensure that this pilot study stays on track and achieves its objectives within the 1-year grant period.

Study Timeline (1-year)

Study Quarterly	Milestones

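### Table 1 puts BIA and MRI after the walk and leg strength tests but the reference DXA before them, so exercise state is confounded with tool in the primary comparison

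*Protocol*

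**What the plan says.** Under Pre-visit requirements the protocol sets a two-hour abstention from exercise: "Participants will not exercise, shower, or use steam rooms or saunas at least two hours before evaluation". The same block covers the overnight fast, clothing and supplements.

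Under In-person Measurements, Table 1 is presented as the running order: "Each procedure and the measurement tool are listed down in sequence". The rows that matter here, with duration and cumulative time where quoted, are:

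- Isotope dose: "Drink Deuterium then Bromide dilutions. 10m 1h10m"
- DXA: "Measure body composition 20m 1h50m"
- Six-minute walk: "Measure distance to complete 6 minutes of walking 20m 3h 20m"
- Leg strength and endurance: "Measure leg strength and endurance 30m 3h 50m"
- Follow-up blood sample, labelled as 4 h after the dose, ending at 4h10
- BIA: "Measure body composition with several devices", ending at 4h30
- MRI of abdomen, pelvis and thigh, ending at 5h10

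BodPod, 3D optical imaging and waist fall between DXA and the walk. The visit schedule under Duration of Study Participation lists walk, strength test, blood sample, BIA and MRI in the same order for both visits. Study Endpoints makes the tool comparison (Aim 1) the primary endpoint and names DXA as the reference for the other methods. The protocol describes no rest period, no varied order and no BIA reading before exercise.

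**The concern.** Aim 1 compares tools within the same person. DXA is always taken before the walk and strength tests, and BIA and MRI always after them. In every participant, at both visits, a BIA-DXA or MRI-DXA difference contains the tool difference plus any effect of recent exercise. The two coincide completely, so no analysis plan can separate them afterwards.

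The exposed measurements are relevant ones. Procedures Involved describes BIA as measuring water inside and outside cells. The strength test loads the upper leg, and MRI then images the thigh for skeletal muscle. The Background cites a 3-compartment model built from air displacement and BIA, and Study Endpoints lists a 3-compartment model among the tools. If it is built that way here, it would combine a BodPod reading taken before exercise with a BIA reading taken after it.

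The protocol itself treats exercise shortly before evaluation as something to avoid, yet it schedules exercise between the reference and two of its comparators.

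**Working it through.** **Inputs.** The 14 durations in Table 1, in minutes: consent 20, clinic 30, weight and height 10, isotope dose 10, questionnaires 20, DXA 20, BodPod 20, 3D imaging 30, waist 20, walk 20, strength 30, blood 20, BIA 20, MRI 40.

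**1. Reproduce the printed clock.** The durations sum to 310 min = 5h10, and all 14 running totals match the printed ones.

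| Slot | Start (min) | End (min) |
|---|---|---|
| Isotope dose | 60 | 70 |
| DXA | 90 | 110 |
| BodPod | 110 | 130 |
| 3D imaging | 130 | 160 |
| Waist | 160 | 180 |
| Walk | 180 | 200 |
| Strength | 200 | 230 |
| Blood | 230 | 250 |
| BIA | 250 | 270 |
| MRI | 270 | 310 |

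**2. Gaps as printed** (start of tool minus end of exercise test).

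- BIA: 250 - 230 = 20 min after strength; 250 - 200 = 50 min after the walk.
- MRI: 270 - 230 = 40 min after strength; 270 - 200 = 70 min after the walk.

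All are below 120 min. Consent is listed for visit 1 only, but dropping it moves every later slot equally and leaves the gaps unchanged.

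**3. The printed clock conflicts with its own blood-sample label.** The blood slot runs 230 - 70 = 160 min to 250 - 70 = 180 min after the dose slot ends, or 170 to 190 min after it starts. That is about 3 h, not 4 h.

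**4. Gaps with the sample held to 4 h and the order kept.** Four hours falls at 60 + 240 = 300 (from dose start) or 70 + 240 = 310 (from dose end). The 20-min blood slot may begin or finish at that point.

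| 4 h counted from | Blood slot | BIA start, gap after strength | MRI start, gap after strength |
|---|---|---|---|
| Dose start | ends at 300 | 300, 70 min | 320, 90 min |
| Dose end | ends at 310 | 310, 80 min | 330, 100 min |
| Dose start | begins at 300 | 320, 90 min | 340, 110 min |
| Dose end | begins at 310 | 330, 100 min | 350, 120 min |

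BIA is within 120 min in every case. MRI reaches 120 min in one.

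**5. What does and does not cancel.** Let d1 and d2 be the exercise shifts in a BIA reading at visits 1 and 2. The BIA-DXA difference at visit 1 carries d1 in full, and at visit 2 it carries d2. The change in BIA carries d2 - d1, which is zero if the shift is constant.

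**6. Proposed order.** BIA 180-200, MRI 200-240, walk 240-260, strength 260-290, sample at 70 + 240 = 310. If the 20-min blood slot begins at 310, the visit ends at 330 = 5h30, which is 20 min over the printed 5h10. On the same reading of 4 h, the current order would end at 330 + 20 + 40 = 390 = 6h30.

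**The case against.** The strongest reply has five parts.

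- **The rule is not broken.** It stands among instructions on what participants do before arriving, and nothing applies it to tests within the visit. This stands. A reader might infer a direct contradiction, but the text supports only a conflict with the rule's evident purpose.
- **The 20 and 40 min gaps are not firm.** They come from a clock that contradicts the 4 h sample. This stands too, which is why the range is given. It does not rescue BIA, which remains within two hours on every reading, and DXA precedes exercise on all of them.
- **Fluid state.** A reader might add that BIA is also distorted by the isotope drink. The documents do not support this: the dose precedes DXA as well, further drinking depends on thirst, and drinks and voids are accounted for by weight.
- **MRI.** The Risks table describes abdominal MRI with a single thigh slice. Nothing in the protocol suggests that a walk or a leg test alters visceral or subcutaneous fat, so the MRI concern is chiefly thigh muscle.
- **Re-ordering has its own price for isotope dilution.** BIA now directly follows the isotope sample; it would instead end 310 - 200 = 110 min before it. The sample would come 310 - 290 = 20 min after strength testing, against 70-80 min if the current order were kept and the sample taken at 4 h (300 - 230 or 310 - 230). On the printed clock it follows strength immediately. This trade-off is real and should be accepted knowingly. It does not outweigh cleaning the comparison with the named reference.

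**Conclusion.** The order confound is real. At both visits the reference DXA is taken before exercise and BIA and MRI after it, so BIA-DXA and MRI-DXA differences in the primary comparison are inseparable from exercise state. This rests only on Table 1 being followed as listed.

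The size of any bias is unknown, because the documents give no figure for the shift. Purely as an illustration, a 1-2% shift on 50 kg of body water would be 0.5-1.0 kg; both inputs are assumptions and nothing here depends on them.

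Two stronger readings are not supported. First, a reader might infer that every other tool precedes exercise. That is wrong: isotope dilution is an Aim 1 tool, and its follow-up sample also comes after the walk and strength tests. Comparisons among DXA, BodPod, 3D imaging and waist are unaffected. Second, a reader might infer that the 6-month change from BIA or MRI is biased. A constant shift cancels there. The protocol hypothesises a fall in strength after surgery, so equal loading at both visits cannot be assumed, but nothing shows that the shift differs between visits.

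For a 20-person exploratory pilot this is a worthwhile and inexpensive correction for measurements still to come, not a defect that invalidates the study.

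**What to change.** In Table 1, move BIA, and MRI if its booking allows, to directly after anthropometrics and before the exercise tests: BIA 3h00-3h20, MRI 3h20-4h00, walk 4h00-4h20, strength 4h20-4h50, with the isotope sample at its stated 4 h after the dose (about 5h10). If the MRI booking cannot move, moving BIA alone still clears the BIA comparison. Make the visit schedule match, and say whether the two-hour rule is meant to apply within the visit.

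The version is dated March 2026 and the Study Timelines section planned baseline collection for late 2025, so some baselines may already exist. Those participants should keep their original order at visit 2, so that their within-person change stays on one footing.

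**Cost.** No new procedure is added. The visit is about 20 min longer than printed and the MRI booking time changes. BIA no longer directly follows the isotope sample, and that sample still follows exercise, as it does now.

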This is a single-center, non-randomized clinical trial to evaluate body composition outcomes in participants undergoing MS. The pilot study will recruit 20 participants with severe obesity undergoing MS.

We will attempt to recruit participants of all racial and ethnic backgrounds. The majority of our participants live in the area surrounding Baton Rouge.

Equitable Selection of Participants: Individuals of either sex or individuals from any social class, are eligible to participate in the study if they are deemed acceptable candidates based on inclusion/exclusion criteria.

Recruitment Methods

The eligible and interested participants in the current study will be recruited at the Metamor Institute, PBRC. Participants should be scheduled for metabolic surgery prior to enrollment.

Once prospective participants are identified, the clinical research coordinator and/or study investigator will contact the potential participant and determine if the participant has any questions regarding the study and/or consent form. The participant's medical history will be reviewed as well as determination of the subject meeting inclusion and exclusion criteria.

After determination of eligibility by the study staff, the participant will be scheduled for a study visit. An email copy or paper copy of the consent form will be provided to the subject that will subsequently be signed upon arrival on the first study day.

Upon arrival on the study day, the informed consent document will be signed, vital signs and body weight/body mass index confirmed. Pregnancy testing will be performed on women of childbearing potential per current PBRC policy.

Duration of Study Participation

Each participant will complete a single study visit that will take approximately 5 hours.

There will be a total of 2 study visits. The first visit will be before MS and the second visit will be 6 months after surgery.

Procedures	Visit #1 (before surgery)	Visit #2 (6 months after surgery)
Informed Consent	X	
Blood taking and urine testing (pregnancy test in women of childbearing age)	X	X
Vital sign	X	X
Drink Deuterium then Bromide dilutions	X	X
Dual-Energy X-ray Absorptiometry (DXA)	X	X
BodPod (Densitometry/ Air Displacement Plethysmography)	X	X
Complete diet, eating habit and physical activity questionnaires	X	X
3D Optical imaging	X	X
Waist Circumferences measurement	X	X
Six-minute Walk	X	X
Leg strength and endurance	X	X
Collect blood samples at 4 hours post (Deuterium then Bromide dilutions)	X	X

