Aim 2: Assess Changes in Body Composition and Muscle Strength Following MS

Rationale: Understanding changes in body composition and muscle strength post-surgery can help improve patient outcomes and tailor post-operative care.

Approach:

Participants: Same cohort as Aim 1.

Measurements: Same cohort as Aim 1

Data Collection: Measure at baseline and 6 months post-surgery.

Analysis: Compare pre- and post-surgery data to evaluate changes in muscle strength and body composition.

Expected Outcome: Patients will experience a reduction in muscle strength, along with a more significant decrease in fat mass compared to muscle mass.

Aim 3: Compare Body Composition Changes Between SG and RYGB Patients

Rationale: Each metabolic surgery procedure may result in varying body composition outcomes. Comparing these can inform surgical decisions and patient counseling.

Approach:

[figure not shown]
Participants: Divide the cohort into two groups based on the type of surgery (SG or RYGB). Each group has 10 participants (5 male and 5 female)

Measurements: Use the same body composition tools as in Aim 1.

Data Collection: Measure at baseline and 6 months post-surgery.

Analysis: Compare body composition changes between the two groups.

Expected Outcome: RYGB patients will experience a greater reduction in subcutaneous, visceral, and total fat compared to SG patients after 6 months

Schematic of Non-Randomized Clinical Trial and Project Aims for BCOMS

Procedures Involved

Details of the procedures for this pilot study are:

Urine Collection (5 minutes): All participants will provide a urine sample to test for urine specific gravity. In addition, a urine pregnancy test will be administered for female participants that are pre and perimenopausal. A negative pregnancy result is required prior to proceeding with the following measurements.

Manual Anthropometry (20 minutes): Weight and height will be measured twice. Circumferences of waist, hip, midarm and midhigh (left and right) will be measured three times and recorded.

Blood draws (15 minutes): Phlebotomist collect blood samples at baseline and again at 4 hours. During the visit, a phlebotomist will complete two blood draws. The blood samples will be completed at the beginning of the visit. Blood samples (3ml) used for the sodium bromide and deuterium at baseline and 4hrs post-dose.

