Deuterium Dilution (4 hours): Deuterium is a stable, non-radioactive isotope of Hydrogen. It is given orally as deuterium oxide and after mixing with body water, it is eliminated from the body in urine, saliva, sweat, etc. Deuterium oxide is handled in the body the same way as water, and it is dispersed through the body within a matter of hours. First, a baseline sample of blood (3 ml) will be collected. Participants will then be given water that's mixed with the weight-appropriate deuterium dose. A blood sample will be collected at 4 hours. A maximum of 2 samples will be collected. If the participant is thirsty during the protocol, study staff will weigh the drink before the participant consumes it. If the participant needs to use the bathroom during the protocol, study staff will record the weight of the

participant prior to and following a void. The samples collected will have the participant ID number, date, and time of collection. All samples will be sent to PBRC for processing.

Sodium Bromide Dilution (4 hours): Extracellular water provides information on nutritional status in health and disease. The dilution of non-radioactive sodium bromide is widely used in clinical research to measure ECW (1-3). A blood sample of 3ml will be collected before ingesting an appropriate amount of sodium bromide based on body weight diluted in deionized water. A blood sample of 3ml will be collected 4 hours after ingestion. During the 4-hour period participants must refrain from eating anything, but they can drink water if needed. Study staff will weigh the drink before the participant consumes it. If the participant needs to use the bathroom during the protocol, study staff will record the weight of the participant prior to and following a void. The samples collected will have the participant ID number, date, and time of collection. All samples will be processed at PBRC.

Vital Signs (5 minutes): Blood pressure and pulse rate will be measured twice and recorded.

6-minute walk (20 minutes): Study Co-Ordinator will time the 6-minute walk of the participant.

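### The Table 1 timetable leaves 2h40 to 3h10 between the isotope drink and the follow-up draw, so it cannot deliver the 4-hour post-dose sample the protocol requires

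*Protocol*

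**What the plan says.** The Protocol gives the 4-hour interval in five places:

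- The visit schedule under Duration of Study Participation: "Collect blood samples at 4 hours post (Deuterium then Bromide dilutions".
- The blood-draw paragraph under Procedures Involved: "Blood samples (3ml) used for the sodium bromide and deuterium at baseline and 4hrs post-dose".
- The deuterium procedure: "A blood sample will be collected at 4 hours".
- The bromide procedure: "A blood sample of 3ml will be collected 4 hours after ingestion".
- The follow-up row of Table 1 itself: "Blood samples follow up (collected at 4h post- dose".

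Table 1 is also a timetable. The text introducing it says "Each procedure and the measurement tool are listed down in sequence", and each row carries a duration and a running total from arrival. The drink row ("Drink Deuterium then Bromide dilutions") closes at 1h10m. The strength row ("Measure leg strength and endurance") closes at 3h50m. The follow-up blood row comes next and closes at 4h10m. BIA and MRI come after it, and the table ends at 5h10m. Duration of Study Participation puts a visit at about five hours.

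The deuterium procedure caps collection at two samples, one before and one after the dose. Study Endpoints lists ECW and TBW among the Aim 1 measurements and isotope dilution among the Aim 1 tools. Aim 1 is the primary endpoint.

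**The concern.** The timetable and the sampling instruction cannot both be followed. The follow-up slot lies around 4 hours after arrival, and the participant does not drink the tracers until an hour into the visit. Visit clock time may have been taken for time since dose, but that is inference. The mismatch does not depend on it.

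At stake is whether the dilution measurements are taken at the stated time, and at the same time for everyone. There is one post-dose sample per visit, so a mistimed draw cannot be replaced by a later one. Staff who work from the clock and staff who work from the row label would draw at different intervals, and this could vary between participants or between a participant's two visits. The dilution procedures require the collection time on each sample. They do not say that the drinking time is recorded, so the actual interval might not be recoverable afterwards.

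**Working it through.** **Inputs.** Row durations and running totals from Table 1, in minutes:

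| Row | Duration | Slot | Stated total |
|---|---|---|---|
| Consent | 20 | 0–20 | 20m |
| Vital signs, blood, urine | 30 | 20–50 | 50m |
| Weight, height | 10 | 50–60 | 1h |
| **Isotope drink** | 10 | **60–70** | 1h10m |
| Questionnaires | 20 | 70–90 | 1h30m |
| DXA | 20 | 90–110 | 1h50m |
| BodPod | 20 | 110–130 | 2h10m |
| 3D optical | 30 | 130–160 | 2h40m |
| Waist | 20 | 160–180 | 3h |
| Six-minute walk | 20 | 180–200 | 3h20m |
| Leg strength | 30 | 200–230 | 3h50m |
| **Follow-up blood** | 20 | **230–250** | 4h10m |
| BIA | 20 | 250–270 | 4h30m |
| MRI | 40 | 270–310 | 5h10m |

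**Step 1: reproduce the table.** All 14 running totals equal the cumulative sum of the durations. The table is additive, so the problem is not a broken row.

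**Step 2: dose-to-draw interval.** Interval = time in the draw slot − time in the drink slot; shortfall = 240 − interval.

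- Drink end to slot opening: 230 − 70 = 160 min (2h40), 80 short.
- Drink end to slot close: 250 − 70 = 180 min (3h00), 60 short.
- Drink start to slot opening: 230 − 60 = 170 min (2h50), 70 short.
- Drink start to slot close: 250 − 60 = 190 min (3h10), 50 short.

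No convention reaches 240. The shortfall is 50 to 80 min, which is 50/240 = 21% to 80/240 = 33% of the stated interval.

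**Step 3: sensitivity.**

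- Procedures Involved gives shorter times for three steps: DXA 10, BOD POD 15 and 3D scan 10 min. With these, drink end to slot opening is 20 + 10 + 15 + 10 + 20 + 20 + 30 = 125 min (2h05). The gap from 4 hours widens.
- At Visit 2 there is no consent step. Both slots move by the same 20 min and the interval is unchanged.

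**Step 4: what honouring 4 hours does to the visit.** A draw 4 h after the drink starts at 60 + 240 = 300 min (5h00) or 70 + 240 = 310 min (5h10).

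- In the listed order, with a wait of 300 − 230 = 70 to 310 − 230 = 80 min, then draw 20, BIA 20, MRI 40: the visit ends at 300 + 80 = 380 (6h20) to 310 + 80 = 390 (6h30).
- With BIA and MRI first: they end at 230 + 20 + 40 = 290 (4h50). The draw starts at 5h00 to 5h10, and the visit ends at 320 to 330 (5h20 to 5h30).

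Both exceed the 5h10m total in Table 1.

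**The case against.** The strongest reply is that the sampling instruction is clear and consistent. The visit schedule, the blood-draw text, both dilution procedures and the table row all say 4 hours. Table 1 is described as a summary, and its times are budgets. Staff who read the row label would wait, and the sample would then be correct.

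Part of this stands. A reader might infer that TBW and ECW will be measured 50 to 80 minutes early, but the document does not establish that. It is what follows if staff keep to the clock. The reply does not remove the contradiction, though. If staff wait, the row order, the absence of a waiting period and the 5h10m total are wrong instead.

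Three stronger readings are also tempting, and the document supports none of them:

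- *The sample precedes equilibration.* The protocol gives 4 hours as a sampling time and never calls it an equilibration time. It says only that deuterium spreads through the body over some hours, which does not show that mixing is incomplete at 2h40 to 3h10.
- *The error is worth a given number of kilograms of fat-free or fat mass.* Any such figure needs an assumed dilution error, body-water mass and hydration factor, none of which the protocol provides. The protocol also does not say that fat mass is derived from dilution, and DXA is its reference standard.
- *The error will not cancel in the 6-month change because surgery alters gastric anatomy.* The protocol says nothing about tracer absorption after surgery.

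**Conclusion.** The point holds as an internal contradiction. As timed, Table 1 gives a dose-to-draw interval of 2h40 to 3h10 against the 4 hours required by its own label, the visit schedule and the procedure text. The shortfall is 50 to 80 minutes whichever end of each slot is used, and no other section resolves it. This rests only on Table 1 being in time order, which the text states, and on its durations.

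Either the single post-dose sample for two Aim 1 measurements is early, or the sequence and visit length are wrong by more than an hour in the listed order (6h20 − 5h10 = 70 min to 6h30 − 5h10 = 80 min). Which of these happens depends on how staff read the table. The effect on TBW or ECW cannot be sized from the document, so the case for correction rests on an unrepeatable sample and a very cheap remedy, not on a demonstrated bias.

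**What to change.** Reconcile Table 1 with the visit schedule, the blood-draw paragraph and the two dilution procedures, so that one dose-to-draw interval applies throughout. If the stated 4 hours is kept, one arrangement that meets it is:

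1. Move BIA and MRI ahead of the follow-up draw; on the Table 1 durations they end at 4h50.
2. Record the drinking time, state whether the 4 hours run from the start or the end of the drink, and schedule the draw from that record (5h00 to 5h10 on the Table 1 clock).
3. Restate the visit length as about 5h20 to 5h30, both in Table 1 and under Duration of Study Participation.
4. Compute the actual dose-to-draw interval for every visit as a data check. Include any visits already completed: this version is dated March 2026, and Study Timelines places baseline collection in October to December 2025.

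Waiting in the present order would also satisfy the 4 hours, but the visit would then run to about 6h20 to 6h30.

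The cost of re-ordering is a visit 10 to 20 minutes longer than the Table 1 total. No procedure or staff is added. Any participant-facing statement of visit length would need the same correction.
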